Category/Group (e.g., adults, controls, parents, children)	Age Range (e.g., 7-12, 13–17, adults)	Maximum Number to be Consented or Reviewed/Collected (include withdrawals and screen failures)	Number Expected to Complete the Study or Needed to Address the Research Question
Adults, with a positive gene test with > 36 CAG repeats within the previous six (6) months	21-85, inclusive	25	20
		- /	

Total: 25

B. Overall Study Sample Size

If this is a multi-site study, provide the total number of subjects to be enrolled from all sites.

[X] Not applicable: This study will only take place at UCI, and does not involve other sites.

Total number of subjects across all sites is 25.

C. Eligibility Criteria

1. Identify the criteria for inclusion and exclusion.

Inclusion criteria:

- Adults of either sex, ages 18 or older.
- Subjects must have clinical findings of Huntington's disease and a confirmatory family history of Huntington's disease, or clinical findings of Huntington's disease and a CAG repeat expansion of > 36.
- Subjects must have a score of \geq 7 on the Total Functional Capacity (TFC) scale.
- Proficiency with written and spoken English and corrected vision or hearing to complete the cognitive testing.
- Subjects must be capable of providing informed consent and complying with study procedures.
- Subjects must be able to take oral medication.
- Good overall health status with no known problems anticipated over the course of the trial.
- Women of child bearing potential (i.e., not postmenopausal or surgically sterile) must have a negative pregnancy test, be non-lactating and use adequate contraception methods during the study. Adequate contraception methods include abstinence, oral, implanted or injected contraceptives (e.g., birth control pills, intrauterine device), barrier (e.g., vaginal ring or diaphragm/cervical cap with spermicide), transdermal patch and/or partner vasectomy. Reliable contraception must be in use 30 days prior to Baseline Visit.

Exclusion criteria:

- History of known sensitivity or intolerance to any fibrate medication.
- Exposure to an investigational medication within the 30 days prior to baseline visit.
- Other major neurological disease [e.g., multiple sclerosis, Parkinson's disease, cortical stroke, etc]
- Clinically significant hepatic disease, gallbladder, or severe renal dysfunction, including primary biliary cirrhosis, and unexplained persistent liver function abnormality.

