- [] At least one member of the study team is fluent in the language that will be used for communication, and that study team member(s) will be available during emergencies.

For all members of the study team responsible for obtaining informed consent from non-English speaking subjects, provide their qualifications to serve in this capacity (i.e. language fluency) in Section 2.

- [] The study team has 24-hour access to a translation service with sufficient medical expertise to discuss the research in this study.
- [] Other (explain): <Type here>

SECTION 6: RESEARCH METHODOLOGY/STUDY PROCEDURES

A. Study Location

Specify where the research procedures will take place (e.g. UCI Douglas Hospital – Cardiac Care Unit, UCI Main Campus Hewitt Hall, UCI Health – Pavilion II, UCI Family Health Center, Anaheim, Irvine High School).

If research activities will also be conducted at non-UCI locations (e.g., educational institutions, businesses, organizations, etc.), Complete Appendix A. Letters of Permission or other documentation may be required (e.g. Off-site Research Agreements or IRB Authorization Agreements).

The study procedures will take place at Gottschalk Medical Plaza or the Institute for Clinical and Translational Sciences (ICTS) in Hewitt Hall.

B. Study Design

1. Include an explanation of the study design (e.g., randomized placebo-controlled, cross-over, crosssectional, longitudinal, etc.) and, if appropriate, describe stratification/ randomization/blinding scheme.

Overall Strategy: We propose to examine the disease-modifying potential of the PGC-1 α activating agent fenofibrate in a pilot randomized, double-blind, placebo-controlled clinical trial for 6-months in 20 newly diagnosed gene positive HD subjects. Subjects who meet our entry criteria will be randomized (3:1) to either 145mg daily fenofibrate or placebo. The main hypothesis being tested is that fenofibrate increases PGC-1 α and slows the progression of HD. Our primary outcome will be change in PGC-1 α RNA and protein levels over the 6-month trial. In secondary analyses, we will examine drug effects on cognitive, psychiatric, and functional outcomes. This pilot clinical study will be conducted by [name].

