- For women of childbearing potential, review of acceptable birth control methods that must be used during the study

All potential participants who meet the eligibility criteria after this screening will be scheduled for the Baseline visit within 14 days.

Baseline Visit.

The following baseline visit procedures will be performed within 14 days from the screening visit:

- Conduct final review of eligibility (prior to first dose). Subjects must continue to meet all inclusion and exclusion criteria at the Baseline Visit.
- Obtain vital sign measurements
- Complete all sections of the UHDRS (Motor, Cognitive, Behavioral, Functional, Independence, and TFC).
- Assess predominant HD symptoms (must be completed by the site investigator)
- Complete Neuropsychological Tests (Hopkins Verbal Learning Test-Revised, Symbol Digit Modalities Test, UHDRS Cognitive, Stroop Word and Benton Judgment of Line Orientation)
- Review concomitant drug usage
- Assess adverse events
- Instruct subject about correct administration of study drug
- Provide instructions to subject and caregiver (if applicable) on study drug consumption, compliance, and reporting of adverse experiences

This visit should take about 2-3 hours.

Following phlebotomy subjects will receive calories and fluids (e.g., energy bar and juice) and then undergo clinical evaluations, including UHDRS, cognitive tests, and CGI-S. Upon conclusion of clinical evaluations the study procedures will be reviewed with the subject and the one month supply of study medication will be provided.

Monthly Visits. The 6, monthly visits will involve a fasting blood draw, a brief clinical examination and completion of an adverse events questionnaire. A pill count will be done to monitor study drug compliance. Monthly visits are expected to last 30 minutes to one hour. The 3- and 6-month visits will include administration of the UHDRS, MoCA, Neuropsychological exams and the CGI.

Randomization. The first 20 participants eligible for the trial after screening will be randomly assigned to either the active drug or placebo group at a 3:1 ratio. Enrollment ID Numbers will be developed by the study statistician and will correspond to specific study drug vials. Study drug will be labeled with a four-digit Enrollment ID Number assigned to that subject.

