We will allow patients using statins to enroll in the study because recent guidelines from the American College of Cardiology and the American Heart Association now recommend the use of these drugs in adults as primary preventative therapy for heart disease.

Blinding. The randomization assignment for each participant will be blinded to all clinical investigators and known only to the study statistician who will perform the randomization and maintain the randomization key. Group assignment will be un-blinded after the clinical trial is complete, or if there is a medical emergency for the participant which requires this.

Study Drug. All subjects will receive a one month supply of study medication from the Study Coordinator at the baseline visit and at subsequent monthly visits for a total of 6 months of drug. All study medications (active drug and placebo) will be prepared in identical appearing capsules. The approved dosing of fenofibrate is in 48mg, 96mg, and 145mg capsules with a maximum dose of 145mg per day. Participants assigned to the active drug group will take a single 145mg capsule of fenofibrate daily during the study and participants assigned to the placebo group will take a single, identical appearing inert capsule daily during the study. We will utilize the maximum tolerated dose for each subject beginning at 145mg per day and reduce the dose if significant side effects are encountered (see Adverse Events).

2. Provide precise definitions of the study endpoints and criteria for evaluation; if the primary outcomes are derived from several measurements (i.e., composite variables) or if endpoints are based composite variables, then describe precisely how the composite variables are derived.

Table	2.	Study	Outcomes
-------	----	-------	----------

Outcome	Туре	Measure
Primary Outcome	PGC-1 α activity	Leukocyte PGC-1a RNA and protein concentrations
Secondary	Fenofibrate	Plasma fenofibrate levels
Outcome		
Secondary	Motor	Unified Huntington Disease Rating Scale (UHDRS)
Outcome		Motor
Secondary	Cognition	Montreal Cognitive Assessment (MoCA)
Outcome		
Secondary	Psychiatric	Unified Huntington Disease Rating Scale (UHDRS)
Outcome		Behavioral
Secondary	Functional	Clinical Global Impression (CGI-I)
Outcome		

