The primary analysis will assess the impact of fenofibrate on leukocyte PGC-1a protein and transcript levels. The effect of fenofibrate on PGC-1 will be analyzed using a repeated measures model. We will use a generalized linear model to examine possible correlations of PGC-1 level with UHDRS Motor change. The UHDRS Motor Scale score change after 6 months of treatment will be examined using an intent to treat principle. We will use a likelihood based mixed effects model, which has greater statistical power and is valid when data is missing at random. Non-random missing data will be examined and analyzed using a pattern mixture model. All analyses will be done by study statisticians using SAS.

2. Describe the primary statistical method(s) that will be used to analyze the primary outcome(s) or endpoints.

PGC-1 measurements. Blood samples will be collected in the morning, after an overnight fast and withholding all morning medications. PGC-1 RNA and protein from peripheral blood mononuclear cells (PMBC's) will be measured by qRT-PCR and enzyme-linked immunosorbent assay (ELISA) respectively. RTPCR will be performed by the ABI PRISM 7900HT Sequence Detection System (Applied Biosystems, Foster City, CA). Each 25µl reaction consists of PGC-1 specific primers (Hs01016719_m1), cDNA template and qPCR gene expression Mastermix (Life technologies). Cycle threshold values for each reaction are adjusted automatically, and the fold changes are determined. The fold-changes values are derived relative to control and are represented as means + SEMs of mRNA expression normalized to ß-actin and comparison made using ANOVA PGC-1 protein expression will also be performed using a PGC-1 ELISA kit (USA biological) as per the instructions

of the manufacturer.

3. Describe the secondary statistical method(s) that will be used to analyze the secondary outcome(s) or endpoints.

UHDRS Motor Scale score change after 6 months of treatment using an intent to treat principle. We will use a likelihood based mixed effects model, which has greater statistical power and is valid when data is missing at random. Non-random missing data will be examined and analyzed using a pattern mixture model. The effect of fenofibrate on PGC-1 will be analyzed using a repeated measures model. We will use a generalized linear model to examine possible correlations of PGC-1 level with UHDRS Motor change.

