4. If appropriate describe secondary or post hoc analyses of primary outcome(s) or other exploratory analysis.

<Type here>

5. Sample Size Determination: Explain how the overall target sample size was determined (e.g., power analysis; precision estimation), providing justification of the effect size for the primary outcome based on preliminary data, current knowledge/literature and/or cost consideration; if appropriate, provide sample size justification for secondary outcomes. Power analysis should (at least) match the primary outcome/endpoint.

Based on a 50% effect size from our preclinical work on MN9D cells, a sample of 15 subjects will provide 80% power at an alpha level of 0.05. HD is a relatively rare genetic disease.

SECTION 7: RISK ASSESSMENT AND POSSIBLE BENEFITS

A. Risk Assessment

- 1. Indicate the appropriate level of review of this study, based upon your risk assessment.
- [X] This study involves greater than minimal risk to subjects and requires Full Committee review. *Skip to Section 7.B.*
- [] This study involves no more than minimal risk and qualifies as **Expedited research**.
- 2. If this study involves no more than minimal risk, provide justification for the level of review and for all applicable Expedited Categories you have chosen.

<Type here>

B. Risks and Discomforts

Describe and assess any reasonably foreseeable risks and discomforts — physical, psychological, social, legal or other. Include an assessment of their expected frequency (e.g., common – 65%, less common – 40%, unlikely – 5%, rare - <1%) and the seriousness (mild, moderate, severe). A bullet point list is recommended. If this study will involve the collection of identifiable private information, even temporarily, for which the disclosure of the data outside of the research could reasonably place the subjects at risk, include the risk of a potential breach of confidentiality.

Risks and side effects related to fenofibrate may include:

Common risks (frequency is 1% to 10%)

- Abdominal pain
- Back pain
- Asthenia (weakness)
- Flu syndrome
- Diarrhea
- Nausea
- Respiratory Disorder
- Rhinitis (nasal allergy)

Less common risks (frequency is 0.1% to 1%)

- Headache
- Abnormal liver function tests
- Constipation
- Hypertension (high blood pressure)
- Alterations in kidney function

Rare (frequency is 0.01% to 0.1%)

- Accidental injury
- Allergic reaction
- Chest pain
- Cyst
- Fever

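### The 80% power claim for 15 subjects is unsupported and is not tied to the randomised comparison of about 15 fenofibrate versus 5 placebo

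*Combined protocol and SAP*

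**What the plan says.** The whole justification is in Section 6, Statistical Considerations, item 5: "Based on a 50% effect size from our preclinical work on MN9D cells, a sample of 15 subjects will provide 80% power", at alpha 0.05, followed by a feasibility remark, "HD is a relatively rare genetic disease". The form's instruction for that item is "Power analysis should (at least) match the primary outcome/endpoint".

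Other parts of the plan bear on it:

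- **Allocation.** Section 6.B.1, Randomization: the first 20 eligible participants are "randomly assigned to either the active drug or placebo group at a 3:1 ratio". The 15 v 5 split follows by arithmetic and is not printed. No blocking is described, so it is approximate.
- **Number needed.** The subject-numbers table in Section 3 enters 20 under "Number Expected to Complete the Study or Needed to Address the Research Question".
- **Primary outcome.** Section 6.B.1: "Our primary outcome will be change in PGC-1"α, RNA and protein, over six months. Table 2 in Section 6.B.2 also names both measures, as "RNA and protein concentrations".
- **Analysis.** Statistical Considerations, item 1: "The effect of fenofibrate on PGC-1 will be analyzed using a repeated measures model". The assay text under item 2 mentions ANOVA.
- **Source of the effect.** Section 1, item 2 describes the MN9D result only as an increase that depends on dose. It gives no percentage, variance or number of replicates.

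**The concern.** A power figure means something only for a stated comparison, effect and variability. Here the 15 equals the inferred fenofibrate arm, whereas the efficacy question is drug against placebo and the placebo arm has about five subjects. A cell-line experiment cannot supply the between-patient SD of leukocyte PGC-1α. It is also unclear whether 50% is half a standard deviation or a 50% rise.

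A reader could take the 80% as applying to the randomised comparison and so misjudge what a null result means. The pilot is also meant to supply effect sizes for a Phase IIb trial (Section 1, item 4; Section 6.B.2), and the plan does not say how precisely 15 v 5 would estimate them.

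**Working it through.** **Inputs from the documents:** power 80%; alpha 0.05; 15 subjects; 50% effect; 20 randomised 3:1, taken as 15 v 5; baseline and six monthly PGC-1α samples. **Not in the documents:** SD, sidedness, effect scale, within-subject correlation. Results are two-sided with one-sided in brackets, use the noncentral t, and take one change value per subject unless stated. SD means the SD of individual change.

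**1. Trying to reproduce the 80% with 50% read as 0.5 SD.**

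- Within 15 subjects: noncentrality = d√n = 0.5 × √15 = 1.94, 14 df. Power is 44% (58%).
- 15 v 5: noncentrality = d√(15 × 5 / 20) = 0.5 × 1.936 = 0.97, 18 df. Power is 15% (24%).

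Neither is near 80%.

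**2. Reading 50% as a 50-point rise over placebo.** At 15 v 5, 80% power needs d = 1.53 (1.335). The largest SD allowed is 50 / 1.53 = 32.7 points (50 / 1.335 = 37.4). Two-sided power over assumed SDs:

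| SD of change (points) | 25 | 30 | 35 | 40 | 50 |
|---|---|---|---|---|---|
| Power at 15 v 5 | 96% | 86% | 74% | 63% | 45% |

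The unstated SD decides the answer.

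**3. If the 80% came from a two-sided within-arm test on 15.** That needs d = 0.778, an SD of 50 / 0.778 = 64 points for a 50-point change. The same effect at 15 v 5 has noncentrality 0.778 × 1.936 = 1.51 and power of about 30%.

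**4. What 15 v 5 delivers on one change value.**

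- Detectable at 80% power, two-sided 0.05: 1.53 SD. With alpha split to 0.025 each for RNA and protein: about 1.71 SD.
- 95% CI half-width: t(0.975, 18 df) × √(1/15 + 1/5) = 2.101 × 0.516 = 1.08 SD.
- 95% CI for the SD: √(18 / chi-square quantiles, 18 df) = 0.76 to 1.48 times the observed SD.

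**5. Allowing for repeated measures.** Assume compound symmetry with correlation ρ, complete data, a constant effect over six visits, and a baseline-adjusted mean of those visits. In units of the single-visit variance, the residual variance is V = (1 + 5ρ)/6 − ρ², and the SD of change is √(2(1 − ρ)). The detectable difference in SDs of change is 1.53 × √(V / (2(1 − ρ))).

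| Assumed ρ | V | √(V / (2(1 − ρ))) | Detectable (SD of change) |
|---|---|---|---|
| 0.3 | 0.327 | 0.483 | 0.74 |
| 0.5 | 0.333 | 0.577 | 0.88 |
| 0.7 | 0.260 | 0.658 | 1.01 |
| 0.9 | 0.107 | 0.730 | 1.12 |

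An effect of 0.5 SD of change lies below every entry, so it stays under 80% power across this range. If the 0.5 were instead in single-visit SDs, ρ = 0.9 would give 0.5 / √0.107 = 1.53, which is 80%. A contrast at month 6 alone would gain less than the averaged visits.

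**The case against.** **It is a pilot in a rare disease.** The form accepts precision or cost as a basis for sample size, and rarity is cited. This stands as a reason for 20 subjects. It does not support a specific 80%, which the plan chose to claim.

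**A 50% rise is the more natural reading.** The RNA result is to be expressed as a fold change, which fits a relative increase better than half a standard deviation. On that reading an SD of up to about 33 points delivers 80% at 15 v 5. This also stands, so the 15% figure must not be quoted as the trial's power.

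**The repeated measures model is more efficient than a t test on one value.** True, and any restated figure should show the range. The gain depends on a correlation the plan does not give.

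Two stronger readings are tempting. A reader might infer that the 80% is false and the trial hopelessly underpowered. The documents do not support that, because some SDs and some correlations do yield 80%. A reader might also infer that the plan names no test or comparator at all. That is true only of the power sentence: the analysis text names a repeated measures model and ANOVA, and placebo is the comparator throughout. Reading 15 as the trial total has little basis, since 20 at 3:1 gives exactly 15 on fenofibrate.

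**Conclusion.** The concern holds as a failure of justification, not as an arithmetic error. The stated power cannot be derived from anything in the documents and is not attached to the comparison the trial randomises. The gap could be large: an effect with 80% power within 15 treated subjects has about 30% at 15 v 5. It could also be nil, if the SD of change is about 33 points or less for a 50-point difference over placebo.

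These sizes rest on t tests with equal variances, an exact 15 v 5 split and no dropout. The repeated measures range also rests on compound symmetry and assumed correlations of 0.3 to 0.9. The data collected are unaffected, and the result can still be read from its confidence interval. The statement should be corrected, but the design need not change on this account.

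**What to change.** Withdraw the 80% statement and replace it with wording such as:

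> With about 15 fenofibrate and 5 placebo subjects and two-sided alpha 0.05, a t test on one change value has 80% power for a between-arm difference of 1.53 SD of change (about 1.71 SD if alpha is split between RNA and protein), with a 95% CI half-width of about 1.08 SD. A baseline-adjusted mean of six monthly visits would detect about 0.74 to 1.12 SD of change for assumed within-subject correlations of 0.3 to 0.9 under compound symmetry.

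Also state what the 15 refers to against the 20 in the Section 3 table, keep the rarity of HD as the feasibility reason, and commit to reporting the between-arm effect and the SD of change with 95% confidence intervals, for RNA and for protein, as inputs for Phase IIb.

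This costs protocol wording only: no extra subjects, visits or assays. The downside is a less favourable stated figure. Keeping the 80% would cost more, because it needs a human SD for each measure and the documents contain none.
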